7.2.1 Primary Safety Variable(s)

Incidence (absolute and percentage) of TEAEs, TEAESIs, TESAEs, and related TEAEs will be calculated on the level of system organ class (SOC) and preferred term (PT). In addition, incidences for TEAE will also be presented by worst intensity and by worst causal relationship. In general, incidences for TEAEs will be reported by the following actual dose groups: 20 U [pooled over stage 1 and stage 2], 50 U, 75 U, 100 U. To explore potential stage effects, incidences for TEAE by worst causal relationship will additionally be provided separately for actual 20 U dose groups from stage 1 and stage 2.¹¹

The following AE summary tables will be created by actual dose group and overall (entire study period), whereby in general the dose groups 20 U pooled, 50 U, 75 U, 100 U will be used:

- TEAEs, subjects with TEAEs and number of TEAEs by SOC and PT.

[figure not shown]
¹¹ This analysis was added after finalization of the CSP.

[figure not shown]
- TEAEs, subjects with TEAEs by PT.
- TEAEs, subjects with TEAEs and number of TEAEs by SOC and PT [REDACTED]
- Non-serious TEAEs, [REDACTED] by SOC and PT.
- TEAEs by worst intensity, subjects with TEAEs.
- TEAEs by worst causal relationship, subjects with TEAEs (20 U stage 1, 20 U stage 2, 20 U pooled, 50 U, 75 U, 100 U).
- Treatment related TEAEs by SOC and PT.
- Treatment related TEAEs occurring between baseline and Day 180 (V9 or End of MP), by SOC and PT.
- Treatment related TEAEs occurring between baseline and End of MP, by SOC and PT.
- TEAEs by worst outcome, subjects with TEAEs.
- TESAEs, subjects with TESAEs by SOC and PT.
- TESAEs, listing of subjects.
- Related serious TEAEs, listing of subjects.
- Deaths, listing of all serious TEAEs leading to death.
- TEAEs leading to discontinuation, listing of subjects.
- TEAESIs, subjects by SOC and PT.
- TEAESIs, listing of subjects

[figure not shown]
Related TESAEs, deaths, TEAEs leading to premature discontinuation and TEAEs related to COVID-19 will be listed only.

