Occurrences of treatment-emergent adverse events (TEAEs), serious TEAEs (TESAEs), treatment-emergent adverse events of special interest (TEAESIs), related TEAEs and related TESAEs by dose group for the entire study period.

An AE is considered treatment-emergent with onset or worsening on or after date of the first administration of investigational product (IP).

Secondary safety variables

Not applicable.

Total number of subjects and number of countries

A total number of 240 subjects will be randomized.

Stage 1: In total 150 subjects: 30 subjects for the dose groups with 20 U and 60 subjects each for 50 U and 75 U (1:2:2 randomization).

Stage 2: In total 90 subjects: 30 subjects for the dose group 20 U and 60 subjects for 100 U (1:2 randomization).

The study will be conducted in the United States of America (USA) and Germany.

Number of study sites

It is planned to conduct the study in approximately 8 sites.

Number of visits

There will be up to 16 site visits during study course.

Investigational product(s), dose, and route of administration

In this study, all subjects will receive active treatment with NT 201 (active ingredient: NT 101, Clostridium botulinum neurotoxin type A (150kDa), free from complexing proteins) injected into the glabellar area after assignment to one of the following dose groups: 20 U, 50 U, or 75 U in stage 1 and 20 U or 100 U in stage 2 at Baseline Visit V2 (Day 1) of the respective stage. Subjects (in stage 1 and stage 2) who have relapsed to baseline status in the MP will have the option to receive a follow-up treatment with the market approved dose of 20 U NT 201 for their GFL between Day 180 and Day 360.

The treatment will be administered to five intramuscular injection sites into the procerus and corrugator muscles.

Statistical analysis methods

Efficacy variables

The efficacy analyses will be based on the full analysis set (FAS).

Primary efficacy variable

The primary endpoint will be described by Kaplan-Meier Curves per group and the respective medians of times.

[REDACTED] pairwise log-rank tests and Cox proportional hazards regression will be applied to compare differences between high dose groups and the 20 U group to explore statistical significance.

Secondary efficacy variables

The secondary duration of effect variables will be analyzed in analogy to the primary variable.

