9.1.1.6 Vital Signs

Vital signs (i.e., blood pressure and heart rate) will be assessed at each visit from the Screening Visit V1 (Day -3 to -14) to Day 180 (V9), and at End of MP. Vital signs will be recorded in sitting or lying position after the subject has rested for at least 5 minutes.

In case on-site visits are not possible due to COVID-19 restrictions, vital signs cannot be assessed.

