10 SAFETY ASSESSMENTS

10.1 Definition of an adverse event

An AE is any untoward medical occurrence in a subject administered a pharmaceutical product. An AE does not necessarily have a causal relationship with the treatment. Thus, an AE can be any unfavorable and unintended sign, symptom, or disease (including intercurrent illness); deterioration of a pre-existing illness; accident; any suspected drug reaction; or a clinically relevant change of laboratory values whether or not considered related to the IP(s) or study procedure.

Changes in efficacy variables (e.g., subject-reported outcome variables [questionnaires and scales] during the course of the study) need not be documented as AEs, because these changes will be recorded as efficacy variables. Elective treatments planned before screening and which are documented in the subject's source data are usually not regarded as AEs.

The period of observation for an AE extends from the time when the informed consent form was signed until the End of MP if no optional treatment was received or the OLEX Follow-up Visit V16 if optional treatment was received (see Section 6.1). Any medical occurrence during the observation period is an AE and has to be documented in the subject's file. For screening failures AEs are not to be documented in the eCRF. For randomized subjects that experienced AEs during the screening period these have to be entered into the eCRF. Non-serious AEs will not be followed up after the End of MP or the OLEX Follow-up Visit V16 if optional treatment was received.

Pre-existing conditions noted in the medical history should not be reported as an AE, unless the condition worsens or the disease reoccurs during the observation period. To determine whether a condition has worsened, it is compared to the condition of the subject at screening. Abnormal laboratory values obtained during the subject's screening period will only meet AE criteria if newly detected and if considered clinically significant. However, if laboratory values resulting from pre-existing conditions worsen to clinical relevance during the course of the study AE criteria are met.

Data pertaining to AEs will be collected during each study visit on the basis of the subject's spontaneous report, through investigator inquiry, or discovered in the course of examinations performed during the visit.

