6.2 Safety Variables

Per CSP version 1.0, it was foreseen to collect all safety data during on-site visits. In amendment 2 of the CSP, the following strategy to mitigate impact of COVID-19 pandemic on safety of study participants and on completeness of safety data was specified: If planned on-site visits cannot be performed due to COVID-19 situation, safety data (AEs, change in medication and non-drug treatment, and occurrence of pregnancy) will be collected via phone calls provided the subject consented. In addition, on-site visits should be performed at the earliest possible date when the subject is able to safely come to the site again.

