7.4.7 Additional analyses due to outbreak of COVID-19 pandemic

Due to the COVID-19 pandemic, a considerable amount of missing data was expected for subjects from stage 2 (see also section 7.4.1). This especially applies to efficacy variables that are based on live assessments by investigators, which cannot be performed remotely. The primary as well as several secondary [REDACTED] parameters would be affected. It should be noted that under specific circumstances, subsequently missing live ratings on the FWS by the investigator are likely to introduce bias to the assessment of the primary and secondary duration of effect variables. If relapse to baseline status was first assessed only after several intermittently missing follow-up visits due to canceled on-site visits, the time to relapse might be overestimated.

[figure not shown]
Data from Main Period of stage 1 are in contrast not affected by this or any other kind of bias caused by COVID-19 pandemic because stage 1 subjects did not miss any MP visits due to COVID-19 outbreak. Therefore, conduct of separate analyses of data from stage 1 and stage 2 subjects might be necessary in addition to pooled analyses as planned for the final analysis of the study; this decision was taken during the BDRM for the final analysis performed on 7-JAN-2021 (see below). However, for reasons outlined in the following, it appeared reasonable to perform an interim analysis of Main Period data from stage 1 as soon as MP data from all stage 1 subjects were available and cleaned.

[figure not shown]

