All study subjects had their Screening visit V1 as well as their Baseline visit V2 when they received study treatment in MP before the first COVID-19 infections occurred in both Germany and the United States (US). The last subject included into this study was screened on 01-OCT-2019 and randomized on 10-OCT-2019. In Germany and in the US, the first COVID-19 cases were notified in January 2020 (Robert Koch Institute, 2020; Holshue et al. 2020). On March 11, 2020, the World Health Organization made the assessment that COVID-19 could be characterized as a pandemic. Due to this temporal sequence of events, it is evident that COVID-19 pandemic could not affect study treatment at Baseline Visit 2. Likewise, an impact of COVID-19 pandemic in terms of heterogeneity of baseline characteristics of subjects included prior to and during the pandemic can be ruled out.

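### Most adverse-event tables set 100 U beside pooled 20 U over the whole study, although only stage 2 was exposed to late COVID-19 visit disruption: split 20 U by stage and add Day 150 tables

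*SAP*

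**What the plan says.** **Allocation.** The protocol synopsis gives "Stage 1: In total 150 subjects: 30 subjects for the dose groups with 20 U and 60 subjects each for 50 U and 75 U", and "Stage 2: In total 90 subjects: 30 subjects for the dose group 20 U and 60 subjects for 100 U". The final analysis pools 20 U across stages unless stated otherwise (SAP 7).

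**Tables.** SAP 7.2.1 lists the AE tables by actual dose group for the entire study period, in general with 20 U pooled. The visible exception is "incidences for TEAE by worst causal relationship will additionally be provided separately for actual 20 U dose groups from stage 1 and stage 2", added to explore stage effects. A table of related events to Day 180 is also listed. SAP 7.2 mentions TEAE incidence by time interval, with no stage columns visible.

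**How AEs are found.** Protocol 10.1 relies on spontaneous report and on events found "through investigator inquiry, or discovered in the course of examinations performed during the visit". SAP 6.2 adds the fallback in a sentence that opens "If planned on-site visits cannot be performed due to COVID-19 situation, safety data (AEs, change in medication and non-drug treatment, and occurrence of pregnancy) will" and goes on to telephone collection from consenting subjects, with a return to on-site visits as early as is safe. Protocol 10.3 keeps the questioning on events of special interest by phone. Protocol 9.1.1.6 states: "In case on-site visits are not possible due to COVID-19 restrictions, vital signs cannot be assessed".

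**Who was affected.** SAP 7.4.7 states that "stage 1 subjects did not miss any MP visits due to COVID-19 outbreak". SAP 7.4.1 expects considerable missing data in stage 2. The COVID-19 sensitivity analysis, and the conclusion of the blind data review meeting, concern the primary efficacy variable (SAP 7.1.1, 7.4.7).

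**The concern.** Safety by dose is part of the primary objective. Any difference in late AE collection between the stages falls entirely on 100 U relative to 50 U and 75 U, and half-way on pooled 20 U. A flat or falling incidence from 75 U to 100 U could then partly reflect how events were collected.

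The design already contains the right comparator. Protocol 6.2 says 20 U was enrolled in both stages for blinding and for comparability of results. The 20 U stage 2 arm was randomised alongside 100 U and followed through the same months. Pooling removes it from view in the visible tables by system organ class (SOC) and preferred term (PT) of TEAEs, related TEAEs, TESAEs and TEAESIs.

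**Working it through.** No stated figure is in dispute. The allocation adds up: 30 + 60 + 60 = 150, 30 + 60 = 90, total 240.

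**1. When stage 2 could be affected.** SAP 7.4.7: "The last subject included into this study was screened on 01-OCT-2019 and randomized on 10-OCT-2019". The dose escalation meeting was on 24-JUL-2019 (SAP 7.4.2). With screening at least 3 days before baseline, and assuming it began after that meeting, the earliest stage 2 injection is 27-JUL-2019. Study day = date − injection date + 1.

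| Date | Last subject | Earliest possible subject |
|---|---|---|
| 11-MAR-2020 (pandemic declared) | Day 154 | Day 229 |
| 30-APR-2020 (amendment 2) | Day 204 | Day 279 |

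The last subject reached Day 150 on 07-MAR-2020 and Day 180 on 06-APR-2020. Subjects randomised after 14-SEP-2019 had Day 180 after 11-MAR-2020, so a Day 180 cut is not fully clear of the disruption. The documents do not date the first visit lost. If disruption began on 1 March, the last subject was at Day 144.

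**2. What a phone contact loses.**
- Physical examination is scheduled at screening and End of MP only (protocol 9.1.1.5).
- Safety laboratory samples are likewise taken at screening and End of MP only (9.1.2.1).
- Vital signs are scheduled up to Day 180 and at End of MP (9.1.1.6).
- By 30-APR-2020 every stage 2 subject was past the Day 180 window (204 > 187). Under amendment 2 the scheduled loss is therefore the End of MP examination, vital signs and laboratory tests, where that visit was missed.
- Also lost are incidental in-person observation and any contact that never took place.

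**3. Illustrative size.** The documents give no late AE rate and no capture rate. Assume 30% true total incidence at every dose, a part L of it late (5 or 10 points), and a share q of late events captured in stage 2.

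- 50 U and 75 U: 30
- 100 U: 30 − L(1 − q)
- Pooled 20 U: 30 − L(1 − q)/2

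| q | L | 100 U | Pooled 20 U | 50 U, 75 U |
|---|---|---|---|---|
| 1.0 | 5 or 10 | 30.0% | 30.0% | 30% |
| 0.9 | 5 | 29.5% | 29.75% | 30% |
| 0.9 | 10 | 29.0% | 29.5% | 30% |
| 0.7 | 5 | 28.5% | 29.25% | 30% |
| 0.7 | 10 | 27.0% | 28.5% | 30% |
| 0.5 | 5 | 27.5% | 28.75% | 30% |
| 0.5 | 10 | 25.0% | 27.5% | 30% |

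For q of 0.5 to 0.7, the loss at 100 U is between 60 × 0.05 × 0.3 = 0.9 and 60 × 0.10 × 0.5 = 3 subjects out of 60. For late events alone, with equal true rates, the ratio of 100 U to 50 U or 75 U is q (0.9, 0.7, 0.5). The ratio to pooled 20 U is 2q/(1 + q) (0.95, 0.82, 0.67).

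**4. With the concurrent comparator.** If 100 U and 20 U stage 2 share the same q, the late-event ratio is q/q = 1.00 whatever q is.

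**5. What the 20 U split can show.** With 30 against 30 subjects, power to detect halved capture is 11% (10% v 5%), 19% (20% v 10%) or 28% (30% v 15%). Detecting 20% v 10% with 80% power would need 199 per stage.

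**The case against.** A reader might infer that stage 2 AEs were collected only by phone from March 2020, that the plan has no control for this, and that 100 U will look too safe. The documents support none of the three.

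- **Phone was a fallback.** It applied only when an on-site visit was impossible and the subject agreed. It comes from amendment 2, dated 30-APR-2020; 11-MAR-2020 is only the pandemic date. Calls fell on planned visit dates and kept the AE and special-interest questioning. Later contacts can still recover earlier onsets.
- **Little scheduled examination was displaced.** V10 to V14 had no scheduled physical examination or vital signs even on site. Protocol 6.2 places peak effect by Day 30, which the last stage 2 subject reached on 08-NOV-2019.
- **Partial controls exist.** There is one stage-split table, a Day 180 table of related events and a time-interval analysis. Parts of SAP 7.2.1 are redacted, and SAP 9 reports new COVID-19 variables with 7.2 among the sections named, so further control cannot be ruled out.
- **Direction is open.** Observation runs from Day 180 to Day 360 depending on relapse, so a longer effect at 100 U would give more time for AEs.

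All of this stands, and it narrows the point to late events and a modest possible shift. It does not remove the confounding of stage with dose. The one stage-split table is by worst causal relationship, the Day 180 table covers related events only, and the other main tables show no split in the visible text. Because safety is descriptive with no inference (protocol 12.4.5), these tables carry the dose comparison.

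**Conclusion.** The concern holds in a limited form. Late AE collection could differ between stage 2 and stage 1, from about Day 154 at the earliest, and the visible SAP controls for this only in part. An undercount at 100 U is possible; its existence, direction and size are not established. Under the stated assumptions it ranges from nothing to 5 percentage points of total incidence (30% to 25.0%), and it is proportionally larger among late events.

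The conclusion rests on three things: the SAP's statement that stage 1 lost no main-period visits to COVID-19, 11-MAR-2020 as the start of disruption, and the visible text only. The remedy does not depend on the direction of any bias. It is worth making because safety by dose is a primary objective and the concurrent comparator already exists.

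**What to change.** In SAP 7.2.1:

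1. In the SOC/PT tables of TEAEs, related TEAEs, TESAEs and TEAESIs, add columns for 20 U stage 1 and 20 U stage 2 beside pooled 20 U. State that 100 U is read first against 20 U stage 2.
2. Add TEAE and TEAESI tables for all doses, restricted to onset up to Day 150, as a supportive cross-stage comparison. Planned observation is at least 180 days for everyone, so collection mode and planned follow-up length then match across doses. Keep the full-period tables. Before fixing the cut, check it against the date of the first COVID-19 missed visit. The match is close but not perfect, since an onset before Day 150 may be reported only at a later contact.
3. Report visits held on site, held by phone and missed, per dose group and stage, from the visit-mode data that SAP 7.4.1 says sites record.

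The cost is SAP wording, extra columns and a few tables, with no new data. The 20 U stage columns hold about 30 subjects each and are descriptive only. Events after Day 150 do not appear in the supportive tables.

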7.2.2 Secondary Safety Variables

Not applicable

[figure not shown]
7.4 Special Statistical/Analytical Issues

[figure not shown]
7.4.1 Discontinuations and Missing Data

[figure not shown]
With relevance to efficacy objectives, the treatment will be applied only once and hence cannot be discontinued. Therefore, no premature discontinuation from treatment can occur. Missing values likewise occur at random or because the subject completes the study early due to relapse to baseline. The latter will not impact the primary analysis of duration of effect since this was completely captured. Hence, for any Kaplan-Meier or Cox regression analysis and inferential statistics, intermittent missing data will be ignored and monotone missingness be considered as censored.

Intermittently missing values due to COVID-19 pandemic (resulting from missing visits not performed due to COVID-19 pandemic or visits performed virtually due to COVID-19 pandemic, thus precluding live assessments by the investigator as needed for the primary efficacy variable) as well as monotonously missing values resulting from premature discontinuation due to COVID-19 pandemic are as well considered missing at random. However, a specific pattern of missing values might introduce bias to assessment of the primary variable of duration of effect: If data are missing from visits directly preceding the visit when relapse to baseline status is observed, time to relapse to baseline status might be overestimated. A sensitivity to assess such impact on missing

values due to COVID-19 pandemic on the primary duration of effect variable is described in section 7.1.1.

Handling of missing values due to the COVID-19 pandemic

Due to the COVID-19 pandemic, a considerable amount of missing data is expected for subjects from stage 2. Restrictions related to COVID-19 in both the US and in Germany (temporarily closed sites, stay-at-home orders, quarantines imposed to subjects suspected to be infected) may make it impossible for many subjects to attend all planned on-site visits. Since live assessments by investigators cannot be performed remotely, this will inevitably lead to missing data.

Handling of missing data due to the COVID-19 pandemic in the final statistical analysis will depend on the number and pattern of missing values, which will be thoroughly described in the clinical study report.

Also, reasons for missing data will be described. As specified in CSP amendment 2, for each planned study visit that was not performed at the study site, the site staff should document whether it was performed as virtual visit due to COVID-19 pandemic, not performed due to COVID-19 pandemic (with specific reason) or not performed (due to other reasons). Also, it should be documented if a subject is discontinued from the study due to COVID-19 pandemic, again with specific reason.

During the BDRM for the final analysis performed on 7-JAN-2021 (see also section 7.1.1 above and section 7.4.7 below), the sensitivity analysis described in section 7.1.1 to account for a specific pattern of missingness due to COVID-19 pandemic was considered adequate and sufficient to assess the impact of COVID-19 pandemic on primary efficacy analysis. No additional sensitivity analyses were deemed necessary by BDRM participants.

7.4.2 *Interim Analyses*

[figure not shown]
Dose Escalation Meeting

A blinded evaluation of safety data was performed on 24th July 2019 in a DEM when all enrolled subjects for stage 1 had their Day 30±7 Follow-up Observational Visit V4 completed. Based on the stage 1 data, a decision to proceed with stage 2 of the study with a dose group of 100 U NT 201 was made. The evaluation included blinded safety data of stage 1 subjects of the 20 U, 50 U, and 75 U NT 201 dose group up to Follow-up Observational Visit V4, Day 30±7.

For this DEM the following data was presented overall for the pooled blinded data:

- Subject disposition and demographic data
- Listings of medical history, concomitant diseases, previous and concomitant treatments
- Incidences of TEAEs, TEAESIs, TESAEs, related TESAEs and related TEAEs by SOC and PT
- Listings of TEAE, TEAESIs, TESAEs, Deaths and AEs leading to premature discontinuation

The DEM received complete blinded safety data of stage 1 subjects of the 20 U, 50 U, and 75 U NT 201 dose group up to Follow-up Observational Visit V4, Day 30±7. Based on the stage 1 data, it was decided to proceed with stage 2 of the study with a dose group of 100 U NT 201.

Interim Analysis after Day 180 of stage 1

An interim analysis of complete 180-day data (V9) of stage 1 was performed. This interim analysis served to get early insights regarding the benefit-risk assessment and duration of effect of the dose groups investigated in the stage 1. However, it was not the aim of this analysis to decide on premature termination of the study.

Data was unblinded for sponsor staff and vendor data management and biostatistics staff only as required for the sake of the interim analysis.

For data of stage 1 until Day 180, the blind was not be broken until a BDRM focusing on the interim analysis had convened, the first version of the SAP had been finalized, and a database snapshot had been saved. After the blind was broken, the statistical analysis of stage 1 Day 180 results proceeded.

The study continued and investigators, subjects, site staff and monitors (except the unblinded monitor responsible for interactive web response system [IWRS] compliance) were kept blinded with regard to stage 1 subject's assignment to treatment groups. Stage 2 subjects were not included in the 180-day interim analysis. The blind for subjects in stage 2 is maintained. Moreover, the blindness of investigators and subjects, site staff and blinded monitor will be maintained throughout for both stages until final unblinding.

For the remaining data, the blind will not be broken until the final BDRM has convened, the final version of the SAP has been finalized, and the database has been closed. After the blind is broken, the overall statistical analysis of results will proceed. The SAP might be amended to stage 2 specific aspects before unblinding of stage 2.

As the blind of the subjects of stage 2 will be maintained and procedures for stage 2 will be very advanced when results are disseminated, there is no impact on validity of stage 2 data and the credibility of study results.

For this interim analysis the following data were be presented based on the data up to Day 180 of stage 1:

- Subject disposition and demographic data
- Primary and secondary duration of effect variables
 - Kaplan-Meier estimates
 - Pairwise log-rank test vs. 20 U group
 - Cox regression results with dose group, FWS score at baseline, and study site¹² as fixed effects
- Investigator's FWS and subject's FWS at maximum frown [REDACTED]: Summary statistics and frequency tables for scores and percentages of subjects fulfilling criteria as defined for secondary [REDACTED] variables including 95% confidence intervals

[REDACTED]

- Listings of medical history, concomitant diseases, previous and concomitant therapies [REDACTED]
- Incidences of TEAE, TEAESIs, TESAEs, and related TEAEs by SOC and PT
- Listings of SAEs, Deaths and AEs leading to premature discontinuation

¹² The term "center" as used in the CSP to refer to this fixed effect was replaced by "study site" to increase consistency with other parts of the CSP and throughout this SAP. The meaning remains the same.

[REDACTED]

For presentation of Kaplan-Meier and Cox regression analyses, the 20 U group of stage 1 served as reference group.

The interim analysis was performed including all data [REDACTED] up to V9 (Day 180±7) from stage 1 whereby End of MP visit was included for subjects who have relapsed to baseline status at V9 (Day 180±7) according to the investigator's assessment on the Facial Wrinkle Scale at maximum frown and completed End of MP at Day 180±7. Information on the main reason for end of study was included only for subjects who terminated the study before V9 (Day 180±7), i.e. if the End of MP Visit was performed at Day 180±7.

Interim Analysis after End of Main Period of stage 1

An interim analysis of complete stage 1 MP data was performed as soon as data until and including the End of MP visit V15 from stage 1 subjects were completely available (except for missingness due to premature study discontinuation or intermittently missing visits). The analysis of stage 1 MP data served to get further insights regarding duration of effect and occurrence of TEAEs over the entire Main Period of up to 360 days. As outlined and substantiated in more detail in the newly added section 7.4.7, this allowed for better-informed decision making during the further conduct of the study in stage 2 under the specific circumstances of the COVID-19 pandemic and related restrictions that might make it difficult or impossible for subjects to further attend on-site visits for a certain period of time.

For the interim analysis of stage 1 at Day 180 (see previous section), the blind had already been broken for sponsor staff and vendor data management and biostatistics staff with regards to all subjects randomized in stage 1. Thus, no new subjects needed to be unblinded for this additional interim analysis at End of MP of stage 1.

Data as needed for the analyses below have been cleaned. After a database snapshot had been saved, the statistical analysis of the entire MP of stage 1 were carried out.

The study continued and investigators, subjects, site staff and monitors (except the unblinded monitor responsible for IWRS compliance) were kept blinded with regards to stage 1 subject's assignment to treatment groups. Stage 2 subjects were not included in the interim analysis of stage 1 MP data. The blind for subjects in stage 2 is maintained. Moreover, the blindness of investigators and subjects, site staff and blinded monitor will be maintained throughout both stages until final unblinding.

For stage 2 subjects, the blind will not be broken until the final BDRM has convened, the final version of the SAP has been finalized, and the database has been closed. After the blind is broken, the overall statistical analysis of results will proceed. The SAP might be amended to stage 2 specific aspects before unblinding of stage 2.

As the blind of the subjects of stage 2 will be maintained and procedures for stage 2 will be very advanced when results of stage 1 MP are disseminated, there is no impact on validity of stage 2 data and the credibility of study results.

For this interim analysis the statistical evaluation were presented based on at least the following data up to End of MP of stage 1:

- Subject disposition and demographic data
- Primary duration of effect variable
 - Kaplan-Meier estimates
 - Pairwise log-rank test vs. 20 U group
 - Cox proportional hazards regression with dose group, center and baseline FWS score at maximum frown as assessed by the investigator as fixed effects
- Incidences of TEAEs, TEAESIs, TESAEs, and related TEAEs by SOC and PT

